## 9. DRUG INFORMATION

### Calcitriol

#### *Name and Chemical Information*

1 $\alpha$ , 25 dihydroxycholecalciferol; 1, 25-dihydroxyvitamin D

#### **Chemical Structure**

Molecular Formula: C27H44O3

Molecular Weight: 416.64

#### **Mechanism of action**

Calcitriol is the primary active metabolite of vitamin D3.

#### **Drug Information**

The calcitriol will be supplied by:

PCCA Professional Compounding Centers of America.  
[name]  
[name]

The Product Formulation involves making a solution of the following:

Calcitriol 22.5mg  
Butylated Hydroxytoluene NF(BHT) 100mg  
Butylated Hydroxyanisole NF(BHA) 100mg  
in 100 mls of Almond Oil NF

Calcitriol (1, 25-dihydroxycholecalciferol) is the biologically active form of vitamin D. It is commercially available as an oral formulation of calcitriol designed specifically for high-dose, intermittent administration. In this protocol it will be studied in individuals at high-risk to develop lung cancer.

Because of the substantial preclinical data documenting the potent anti-cancer activity of calcitriol, clinical studies were conducted in various solid tumors with the currently marketed formulation of calcitriol using various routes and regimens. While efficacy was suggested in

I 90206 Amendment # 18

several studies, hypercalcemia was dose limiting in these studies. Moreover, plasma levels did not reach those that would be predicted to have anti-cancer activity.

Investigators discovered that intermittent dosing with calcitriol permits substantial dose escalation. The maximum dose of calcitriol tested was 2.8 µg/kg PO. Plasma calcitriol reached a plateau at doses  $\geq$  0.5 µg/kg PO at levels predicted to be associated with anti-cancer activity without causing dose limiting hypercalcemia. The safety of 0.5 µg/kg calcitriol PO qw was supported by clinical data in over 70 subjects with prostate cancer in three Phase 2 studies. The efficacy of calcitriol was suggested by open-label studies in subjects with AIPC when the drug was administered as either a single agent or in combination with docetaxel.

A Phase 1, multicenter, open-label, dose escalation study of DN-101 was carried out to evaluate the safety, tolerability, and PK of DN-101 (another formulation of calcitriol) in 38 subjects with advanced malignancies. An initial dose of up to 165 µg DN-101 PO was not associated with DLTs, so the MTD was not determined. The MTD for repeat weekly dosing in this study was defined as 45 µg PO qw based on the occurrence of transient, asymptomatic Grade 2 hypercalcemia in two subjects who were treated at 60 µg PO qw for nine weeks. The PK of DN-101 was linear and predictable; there was no evidence of saturation of absorption.

Enrollment and treatment in a Phase 2 study of DN-101 in subjects with MDS has been completed. DN-101 was well-tolerated in the 37 subjects treated in this study. The study was closed to further enrollment when the Simon optimal two-stage analysis, which allowed an early study stop if the true rate of erythroid response was  $\leq$  30%; did not demonstrate the pre-specified number of responses for allowing continuation of the study.

**Risks to Subjects Participating in Clinical Studies of Calcitriol Observed Risks:** In monotherapy studies in subjects with malignancies, calcitriol has been well-tolerated. Low grade hypercalcemia (generally Grade 1) was the most commonly reported adverse event (AE) in 22% of subjects. Two of 6 subjects treated with 60 µg DN-101 weekly in the Phase I study and 3 of 37 subjects with MDS treated with 45 µg DN-101 weekly developed transient Grade 2 hypercalcemia. Other commonly reported AEs of low grade (Grade 1) include fatigue (14%), nausea (6%), increase in alanine aminotransferase (ALT) (5%), increase in serum creatinine (5%), hyperglycemia (5%), and anorexia (5%). Three different subjects reported a Grade 3 hyponatremia, proteinuria, or hypercholesterolemia, and one subject reported a Grade 4 hypercholesterolemia.

**Adverse Events Related to Calcitriol:** Based on the available safety data, the following treatment emergent AEs classified by participating Investigators as possibly or probably related to calcitriol have been reported for subjects treated with calcitriol in clinical studies. Most of these AEs were Grade 1 or 2; calcitriol -related Grade 3 or 4 AEs were rare.

1. ***Blood and lymphatic system disorders:*** anemia NOS, leukopenia NOS, neutropenia, thrombocytopenia, disseminated intravascular coagulation
2. ***Ear and labyrinth disorders:*** fortification spectra, ear congestion
3. ***Eye disorders:*** glaucoma NOS, conjunctivitis, lacrimation increased, vision blurred

4. **Gastrointestinal disorders:** abdominal pain NOS, constipation, diverticulitis NOS, dyspepsia, nausea, vomiting NOS, diarrhea NOS, stomatitis, abdominal pain upper, loose stools, dry mouth, cheilitis, retching
5. **General disorders and administration site conditions:** asthenia, fatigue, pain NOS, chest discomfort, lethargy, edema NOS, edema peripheral, infusion site reaction, mucosal inflammation NOS, pyrexia
6. **Hepatobiliary disorders:** hyperbilirubinemia
7. **Infections and infestations:** pneumonia NOS, oral candidiasis
8. **Investigations:** international normalized ratio increased, alanine aminotransferase increased, AST increased, blood albumin decreased, blood bilirubin increased, blood creatinine increased, blood phosphorous increased, crystal urine, crystal urine present, blood cholesterol increased, hemoglobin decreased, lymphocyte count increased, urine calcium increased, albumin urine present, blood phosphorous decreased, blood urea increased, creatinine renal clearance decreased, platelet count increased, protein total decreased, weight decreased
9. **Metabolism and nutrition disorders:** hypercalcemia, hyperglycemia NOS, hyperkalemia, hyperphosphatemia, hyponatremia, hypophosphatemia, hyperuricemia, appetite decreased NOS, polydipsia, dehydration, hypocalcaemia, hypoproteinemia, anorexia, hypercholesterolemia, hypoalbuminemia, hypokalemia
10. **Musculoskeletal and connective tissue disorders:** myalgia, arthralgia, joint stiffness, back pain, bone pain, muscle weakness NOS
11. **Nervous system disorders:** ataxia, dysphonia, headache, dizziness, carpal tunnel syndrome, dysgeusia, dysaesthesia, hyperesthesia, hypoesthesia, paraesthesia
12. **Psychiatric disorders:** anxiety, depression
13. **Renal and urinary disorders:** nephrolithiasis, polyuria, renal impairment, proteinuria, micturition frequency decreased, urinary incontinence
14. **Respiratory, thoracic and mediastinal disorders:** hiccups, pneumonitis NOS, pulmonary embolism, cough, dyspnea exertional, epistaxis, nasal congestion, pharyngolaryngeal pain, postnasal drip, rhinorrhea
15. **Skin and subcutaneous tissue disorders:** pruritus, ecchymosis, contusion, rash NOS, dry skin, erythema, nail discolouration, nail disorder NOS, night sweats, rash maculo-papular, sweating increased
16. **Vascular disorders:** flushing, hypertension NOS, hypotension NOS

#### Risks Warranting Further Discussion:

1. **Hypercalciuria:** Many subjects treated with calcitriol develop hypercalciuria (elevated urine calcium) but acute nephrolithiasis has been very rare. The risk of nephrolithiasis due to hypercalciuria is minimized by increasing fluid intake.
2. **Hypercalcemia:** Hypercalcemia has been identified as the DLT in non-clinical and clinical studies of calcitriol, and occasional subjects taking calcitriol have had Grade 1 or 2 hypercalcemia. In the Phase 1 study of calcitriol in subjects with advanced malignancies, transient asymptomatic hypercalcemia (Grade 2) occurred in two subjects who received 60 µg calcitriol PO qw for nine weeks. The risk of hypercalcemia is minimized by increasing fluid intake, monitoring serum calcium, evaluating symptoms of hypercalcemia, excluding certain medications or supplements, and excluding subjects with a history of cancer-related hypercalcemia. Long-standing hypercalcemia may result in hypercalcemic nephropathy (interstitial

nephritis), a disease characterized by loss of distal tubule and collecting duct function, a reduction in glomerular filtration rate, and tubulointerstitial damage. Early recognition is important because damage can often be arrested or even reversed with discontinuation of the offending agent. Therefore, periodic monitoring of serum creatinine is recommended for subjects receiving high-dose calcitriol, including calcitriol. The interstitial nephritis seen in the 28-day repeated dose toxicity study of calcitriol in dogs was consistent with hypercalcemic nephropathy.

3. **Transient Renal Insufficiency:** Occasional subjects have had elevations of BUN or serum creatinine, or decreased creatinine clearance while taking calcitriol. The risk of renal toxicity due to calcitriol is minimized by excluding subjects with  $\geq$  Grade 2 elevations of serum creatinine and monitoring renal function during clinical studies with calcitriol.
4. **Hyperuricemia:** The possibility that calcitriol causes hyperuricemia cannot be excluded at this time. In the Phase 2/3 AIPC study (Study DN101-002), Grade 3 or 4 hyperuricemia was reported for two subjects (1.6%) in the group treated with calcitriol and docetaxel; hyperuricemia was not reported for subjects treated with docetaxel and placebo.
5. **Disseminated Intravascular Coagulation:** The possibility that calcitriol may cause disseminated intravascular coagulation cannot be excluded at this time. In the Phase 2/3, AIPC study (Study DN101-002) fatal disseminated intravascular coagulation, deemed related to study drug by the investigator occurred in one subject.
6. **Calcifications of soft tissue:** The possibility that repeat chronic dosing with high-dose calcitriol causes calcification of soft tissues cannot be excluded at this time.

**Overdose:** There is no specific antidote to calcitriol. If overdose were suspected, administration of study drug, calcitriol, should be stopped and general supportive measures instituted, including close monitoring of arrhythmias and serum calcium. The risk of overdose is minimized by the standard dose and written dosing instructions for subjects.

**Administration:** Total duration of therapy will be 3 months. Take one capsule of study drug every other week for a total of 3 months. Patients should be instructed to maintain adequate fluid intake.

**Availability:** calcitriol is a new formulation of calcitriol. For this study a 45 mcg capsule will be dispensed.

**Storage:** calcitriol should be protected from light and stored in the refrigerator.

**Potential Risks:** Potential risks from the intervention are minimal. The most prominent risks are those associated with the potential for hypercalcemia. A bronchoscopy will be performed at the end of the 3-month intervention. This is generally a safe and painless procedure, performed under sedation. The risks associated with bronchoscopy include the following: bleeding (usually mild and self-limiting), drug reaction from sedation, infection – pneumonia or bronchitis (rare), collapse of the lung (pneumothorax) (rare with endobronchial biopsies), and wheezing, breathing trouble or a low oxygen level. These problems are uncommon and are entirely treatable. There is a possible, but rare risk of death with bronchoscopy. Additional minimal risk is associated with blood collection, as

I 90206 Amendment # 18

infection and bruising is possible at the point of needle insertion and induction of sputum. These procedures are part of the routine screening for lung cancer. Potential risks of calcitriol administration include hypercalcemia and hypercalcuria.

**Procedures for Protecting against Potential Risks:** It is unlikely that participants will display symptoms of hypercalcemia. However, all adverse and serious adverse events will be reported to the IRB, FDA and NCI. Minimal risks are associated with blood sample collection. These potential risks will be fully described in approved consent forms.

**Anticipated Benefits versus Potential Risks:** Benefits from this study include lung cancer screening with bronchoscopy and evaluation of premalignant lesions of the lung. While it is hypothesized that calcitriol will positively modulate the biomarkers for lung cancer (and presumably risk associated with lung cancer), this cannot be viewed as a benefit of the study. Society as a whole will benefit from the knowledge gained in this study, as the toxicity profile in non-cancer patients will be better understood. Given the low level of risk for participants in this trial, the costs and risks are justified.

## 10. DATA SAFETY MONITORING

This project is a Pilot study and the DSMB will perform the function of data safety monitoring.

The main goals of this monitoring process will be to 1) evaluate the conduct and recruitment progress of the trial and to assure compliance with eligibility requirements; 2) to evaluate all adverse and serious adverse events that were associated with participation in the trial, including events related to procedures and treatment; 3) to oversee the database managements and integrity; 4) to review interim analyses performed by the study statistician regarding effectiveness of randomization and distribution of adverse events.

## 11. ADVERSE EVENTS AND SERIOUS ADVERSE EVENTS REPORTING

The descriptions and grading scales found in the CTEP Version 4 of the NCI Common Terminology Criteria for Adverse Events (CTCAE) will be utilized for AE reporting. CTEP Version 4 of the CTCAE is identified and located at:

[http://ctep.cancer.gov/protocolDevelopment/electronic\\_applications/ctc.htm](http://ctep.cancer.gov/protocolDevelopment/electronic_applications/ctc.htm).

AEs not covered by specific terminology listed should be reported with common medical terminology, and documented according to the grading scales provided in the CTCAE Version 4.

The relationship of event to study drug will be documented by the Investigator as follows:

- **Unrelated:** The event is clearly related to other factors such as the participant's clinical state, other therapeutic interventions or concomitant drugs administered to the participant.
- **Unlikely:** The event is doubtfully related to investigational agent(s). The event was most likely related to other factors such as the participant's clinical state, other therapeutic interventions, or concomitant drugs.
- **Possible:** The event follows a reasonable temporal sequence from the time of drug administration, but could have been produced by other factors such as the participant's clinical state, other therapeutic interventions or concomitant drugs.

- **Probable:** The event follows a reasonable temporal sequence from the time of drug administration, and follows a known response pattern to the study drug. The event cannot be reasonably explained by other factors such as the participant's clinical state, therapeutic interventions or concomitant drugs.
- **Definite:** The event follows a reasonable temporal sequence from the time of drug administration, follows a known response pattern to the study drug, cannot be reasonably explained by other factors such as the participant's condition, therapeutic interventions or concomitant drugs; AND occurs immediately following study drug administration, improves upon stopping the drug, or reappears on re-exposure.

## 11.1 Reporting Adverse Events

**Table 1 Guidelines for Routine Adverse Event Reporting for Pilot, Phase 2, and Phase 3 Studies (Regardless of Expectedness)**

Attribution	Grade 1	Grade 2	Grade 3	Grade 4
Unrelated			X	X
Unlikely			X	X
Possible	X	X	X	X
Probable	X	X	X	X
Definite	X	X	X	X

Routine AEs occurring between the start date of intervention until 30 days after the last intervention or until the event has resolved, the study participant is lost to follow-up, the start of a new treatment, or until the study investigator assesses the event(s) as stable or irreversible, will be reported. New information will be reported after it is received.

As requested by the FDA, final reporting of AEs will include all AEs regardless of attribution.

## 11.2 Serious Adverse Events

### 11.2.1 Definition

A serious adverse event (SAE) is any adverse event (experience) that in the opinion of either the investigator or sponsor results in **ANY** of the following:

- Death.
- A life-threatening adverse event (experience). Any AE that places a participant or participant, in the view of the Investigator or sponsor, at immediate risk of death from the reaction as it occurred. It does **NOT** include an AE that, had it occurred in a more severe form, might have caused death.
- Inpatient hospitalization or prolongation of existing hospitalization (for > 24 hours).
- A persistent or significant incapacity or substantial disruption of the ability to conduct normal life functions.
- A congenital anomaly or birth defect.

- Important Medical Event (IME) that, based upon medical judgment, may jeopardize the participant and may require medical or surgical intervention to prevent one of the outcomes listed above.

### **11.2.2 Reporting Serious Adverse Events**

All new SAEs occurring from the date the participant signs the study consent until 30 days after the last intervention or a new treatment is started, whichever comes first, will be reported. The RPCI SAE Source Form is to be completed with all available information, including a brief narrative describing the SAE and any other relevant information.

SAEs occurring after the 30 day follow-up period that the investigator determines to be possibly, probably or definitely related to the study intervention should be reported.

SAEs identified as an Unanticipated Problem by the Investigator must be reported. Please refer to Section 11.3 for details on reporting Unanticipated Problems.

### **11.2.3 Follow-Up for Serious Adverse Events**

All related SAEs should be followed to their resolution, until the study participant is lost to follow-up, the start of a new treatment, or until the study investigator assesses the event(s) as stable or irreversible. New information will be reported when it is received.

. Patients will be removed from study for any of the following reasons: Any grade  $\geq$  3 regardless of attribution; a grade 2 that persists for more than two weeks; interim development of new malignancy (lung or extra pulmonary); or withdrawal of consent. Patients will not be given a dose reduction.

## **11.3 Unanticipated Problems**

### **11.3.1 Definition**

An Unanticipated Problem (UP) is any incident, experience, or outcome that meets all of the following criteria:

- Unexpected (in terms of nature, severity, or frequency) given:
  - a) The research procedures that are described in the study-related documents, including study deviations, as well as issues related to compromise of participant privacy or confidentiality of data.
  - b) The characteristics of the participant population being studied.
- Related or possibly related to participation in the research (possibly related means there is a reasonable possibility that the incident, experience, or outcome may have been caused by the procedures involved in the research).
- Suggests that the research places participants or others at a greater risk of harm (including physical, psychological, economic, or social harm) than was previously known or recognized and if in relation to an AE is also deemed **Serious** per **Section 0**.

I 90206 Amendment # 18

### **11.3.2 Reporting Unanticipated Problems**

Unanticipated problem reporting will begin at the time of participant consent. The Unanticipated Problem Form will be submitted to the CRS Compliance Office within 1 business day of becoming aware of the Unanticipated Problem.

When becoming aware of new information about an Unanticipated Problem, submit the updated information to CRS Compliance with an updated Unanticipated Problem Form. The site Investigator or designated research personnel will report all unanticipated problems, whether related or unrelated to the investigational agent(s) to the **IRB in accordance with their local institutional guidelines.**

### **11.4 FDA Reporting**

When RPCI is the IND holder the following describes the FDA reporting requirements by timeline for AEs and new safety findings that meet the criteria outlined below:

#### **Within 7 Calendar Days**

Any adverse event that meets **ALL** the following criteria:

- Related or possibly related to the use of the study drug;
- Unexpected; and
- Fatal or life-threatening.

#### **Within 15 Calendar Days**

Any adverse event that meets **ALL** the following criteria:

- Related or possibly related to the use of the study drug;
- Unexpected; and
- Serious but not fatal or life-threatening;

Or, meets **ANY** of the following criteria:

- A previous adverse event that is not initially deemed reportable but is later found to fit the criteria for reporting (report within 15 days from when event was deemed reportable).
- Any findings from other studies, including epidemiological studies, pooled analysis of multiple studies, or other clinical studies conducted with the study drug that suggest a significant risk in humans exposed to the drug.
- Any findings from animal or in vitro testing that suggest a significant risk for human participants including reports of mutagenicity, teratogenicity, or carcinogenicity or reports of significant organ toxicity at or near the expected human exposure.
- Any clinically important increase in the rate of occurrence of a serious, related or possibly related adverse event over that listed in the protocol or investigator brochure.

Sponsors are also required to identify in IND safety reports, all previous reports concerning similar adverse events and to analyze the significance of the current event in the light of the previous reports.

## Reporting Process

The principal investigator or designee will complete and submit a FDA Form 3500A MedWatch for any event that meets the above criteria. Forms will be submitted to the CRS Compliance Office via email to [[contact]](mailto:[contact]).

## 12. STATISTICAL ANALYSIS

**PK/PD Modeling** - Using a sequential approach (136), a PK/PD structural model will be developed for calcitriol, based on toxicity responses in previous trials. A variety of compartmental population pharmacokinetic structural models will be evaluated to characterize the serum concentration versus time profile following the oral administration of calcitriol. The physiologic pharmacokinetic models explored will be described by the estimation of mean structural model parameters (e.g., plasma volumes of distribution and clearances), the magnitude of inter-individual variability (IIV) in these parameters, and the magnitude of residual variability (RV). To date, a population PK model of calcitriol has not been developed but prior experience of [name] revealed that plasma concentrations may either follow a mono- or biexponential decay. Thus, it is anticipated that the appropriate PK model will initially include either a one- or two-compartment model with first-order absorption and (linear) elimination. The PK model could expand to include mechanistic attributes, such as a receptor-mediated clearance mechanisms since calcitriol binds to the VDR receptor and may in part, get internalized as a complex, undergoing receptor-mediated clearance as one of the primary clearance mechanisms. As a result, a series of more complex PK models may be sequentially evaluated if required to adequately describe the pharmacokinetic profile of calcitriol.

According to the basic tenets of target-mediated drug disposition, distribution phases for lower doses are expected to be steeper than that of larger doses. Some compounds that exhibit such behavior also may show regions of convexity in various sections of the plasma concentration-time curve at relatively high doses. If needed, the unique incorporation of receptor-mediated disposition will represent a more mechanistic model to examine the biodisposition of calcitriol following oral administration. Patient demographics, racial group, along with CYP24A1 phenotype, smoking status, and other laboratory measurements will be evaluated as potential patient covariates that contribute to the inter-individual variability

in pharmacokinetics. Typical metrics of model predictive performance will be used to assess the accuracy and precision with which the best model predicts the calcitriol concentrations, including: traditional global metrics, such as predicted area under the concentration-time curves, apparent oral clearance, apparent volume of distribution, terminal elimination half-life, and other PK parameters, will be compared to values obtained

[figure not shown]

Fig. DM1. General model of target-mediated drug disposition.

from a non-compartmental analysis of the raw data. The final model will be used to conduct simulations to predict pharmacokinetic outcomes and the time-course of inaccessible system variables, as well as providing suitable driving functions for the development of mechanism-based pharmacokinetic-pharmacodynamic models of toxicity endpoints (137, 138).

I 90206 Amendment # 18

Subsequently, a population PK/PD model will be developed to describe the potential relationship between calcitriol exposure and toxicity endpoints, such as hypercalcemia, as indicators of pharmacodynamic response. This analysis will include both structural model development and evaluation of the influence of a limited number of patient covariates, such as patient demographics along with EGFR and smoking status, on the variability in select PK/PD parameters. The relationship between calcitriol concentrations and toxicity endpoints will be explored graphically and various structural models will be applied to the data and evaluated. It is assumed that a sigmoid- $E_{max}$  model or an effect-site PK/PD model, accounting for severity in graded response of the particular toxicity endpoint, may be appropriate to describe the PK/PD relationship. Similar to the PK model development, criteria such as the precision of parameter estimates, magnitude of residual variability and goodness-of-fit will be utilized for PK/PD model selection.

**Optimal Biologic Concentration Determination** - The optimal biologic concentration will be defined as the steady state concentration range that is associated with less than grade 2 toxicity and leads to target inhibition in 90% or greater of patients. Because there are inter-individual variations in absorption and metabolism of calcitriol, a more rational approach will be to evaluate the feasibility of relating concentrations of calcitriol rather than administered dose, to pharmacodynamic markers and toxicity. Thus, we will examine the relationship between exposure levels (Cp or AUC) of calcitriol with pharmacodynamic endpoints and polymorphisms in CYP24A1 and calcitriol metabolizing enzymes. Determining the strength and direction of the association between genotype(s), PD endpoints and calcitriol exposure levels will allow the construction of a preliminary model that will allow personalized dosing to a target drug exposure range (Cp or AUC) for validation in future chemoprevention studies. Based on these data, patients could be initially started on therapy on a non-toxic median dose that leads to target exposure levels. Eventually, doses could be adjusted during treatment to reach target concentrations, as is done with other drugs that have narrow therapeutic indexes such as vancomycin and busulfan for bone marrow transplantation.

We will test the null hypothesis that the proportion of grade 3-4 toxicities or grade 2 toxicities that persist more than two weeks will be 10% versus the one-sided alternative that the proportion of these toxicities will be greater than 10%. An interim analysis will be performed after the first 20 subjects on calcitriol have completed the study. The study can be stopped early at the interim point and the null hypothesis will not be rejected if  $\leq 1$  toxicity is observed, at which time the DSMB will summarize the findings and the results, including all toxicity reports will be submitted to the FDA. Otherwise, the full 40 subjects will be recruited into the study. At the end of the study period, we will again either reject the null hypothesis (if 8 or more DLT toxicities are observed) or not reject the null hypothesis if 7 or less toxicities are observed.

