**Primary Endpoints:**

To determine the number of patients with Grade III-IV toxicities or any Grade II toxicities *that last more than two weeks* associated with a 45 mcg dose of calcitriol administered every other week (QOW) in this population of patients at high risk of lung cancer.

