**Brief Statistical Section:**

We will test the null hypothesis that the proportion of grade 3-4 toxicities and grade 2 toxicities lasting more than 2 weeks will be 10% versus the one-sided alternative that the proportion of grade 3-4 toxicities will be greater than 10%. Given a sample size of n=40, assuming an alpha level 0.05, we will have 80% power to detect the proportion of toxicities of 15% or larger. An interim analysis will be performed after the first 20 subjects on calcitriol have completed the study. The study can be stopped early if the requirements of the null hypothesis (that this dose of calcitriol dose not result in an excess of DLT reports) are met that  $\leq 1$  toxicity is observed. After a full review of the data is completed by the DSMB the results will be reported to the FDA. Otherwise, the remaining 20 subjects on calcitriol will be recruited and treated at the end of the study period (3 months), at which point we will either reject the null hypothesis (if 8 or more toxicities are observed) or not reject the null hypothesis if 7 or less toxicities are observed.

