### 3. METHODS

#### 1. STUDY PURPOSES AND OBJECTIVES

The **Primary Hypothesis** for this study is that high-dose calcitriol 45 mcg. QOW will be well tolerated in a group of patients at high risk of lung cancer.

The **Primary Objectives** for this trial are as follows:

1. **To establish the safety of a 45 mcg dose of oral calcitriol QOW in non-cancer patients.** Forty patients from the RPCI high risk lung cancer cohort will be recruited to 45 mcg of oral calcitriol QOW (n=40) for a period of 3 months. All adverse events and serious adverse events will be reported to the FDA at the end of the study, regardless of relationship to the expected side effects of calcitriol. Patients will be on the study for 3 months. When the first 20 patients on calcitriol have completed the 3-month treatment, an interim analysis will be performed to determine the degree of dose-limiting toxicities associated with every other week administration.

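### The removal rule for grade 3 or worse toxicity contradicts itself on attribution, and the attribution basis of the primary toxicity count is left open

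*Combined protocol and SAP*

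**What the plan says.** **Removal.** Section 5.0 speaks twice. The Toxicity Monitoring paragraph removes a patient for grade 3 or worse toxicity whatever its cause. The numbered Removal from Study list that follows limits this to grade 3 or worse events related to the drug. Section 11.2.3 restates the reasons for removal and again makes attribution irrelevant.

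**Primary count.** The abstract's Primary Endpoints counts patients with grade III-IV toxicities, or grade II toxicities persisting beyond a fortnight, in each case "associated with a 45 mcg dose of calcitriol administered every other week (QOW) in this population of patients at high risk of lung cancer". Section 3 uses similar words for the interim: "an interim analysis will be performed to determine the degree of dose-limiting toxicities associated with every other week administration". The null in section 12 is that "the proportion of grade 3-4 toxicities or grade 2 toxicities that persist more than two weeks will be 10" per cent, and the abstract's Brief Statistical Section has "the proportion of grade 3-4 toxicities and grade 2 toxicities lasting more than 2 weeks will be 10" per cent; neither names an attribution level. The trial may stop after 20 patients with at most one toxicity. At 40 patients section 12 will "reject the null hypothesis (if 8 or more DLT toxicities are observed". DLT is not defined for this trial. The Brief Statistical Section also glosses the null as the dose producing no surplus of DLT reports.

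**Reporting.** Section 3 says that all adverse events "will be reported to the FDA at the end of the study, regardless of relationship to the expected side effects of calcitriol". Section 11.1 says: "As requested by the FDA, final reporting of AEs will include all AEs regardless of attribution". Section 11 sets up a five-level attribution scale from unrelated to definite, but nothing says which levels enter the count.

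**The concern.** Site staff cannot apply the removal rule as written. A patient with a grade 3 event judged unrelated must leave under two statements and is not removed under the third, so the inconsistency affects who continues treatment.

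The open attribution basis affects what the trial concludes. With no control arm, an all-cause count adds background events to drug-related ones, and the two counts can fall on different sides of 1 of 20 or 8 of 40. Bronchoscopy shows how this could arise. Eligibility asks for one within 3 to 4 months of enrolment, and section 11.1 collects adverse events until 30 days after the last intervention. A complication could fall inside that window, and nothing says whether it counts. If the basis is not fixed beforehand, it can be chosen once the events are known.

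**Working it through.** **1. Removal statements side by side (grade 3 or worse)**

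| Place | Attribution needed for removal | Patient with an unrelated grade 3 event |
|---|---|---|
| Section 5.0, Toxicity Monitoring | none | removed |
| Section 5.0, Removal from Study list, item 1 | related to drug | not removed by this item |
| Section 11.2.3 | none | removed |

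All three treat persistent grade 2 toxicity alike. The conflict is confined to grade 3 or worse.

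**2. Does any text fix the count?** The phrase *associated with* does not. Section 10 uses it broadly, for events "associated with participation in the trial, including events related to procedures and treatment", so it may mean caused by the drug or merely occurring on study. The reporting and monitoring statements in sections 3, 5.0 and 11.1 disregard attribution, but they do not say what is compared with the two limits or what the 10% describes.

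**3. The plan's own rule.** Inputs from section 12: null 10%, stop permitted at 1 or fewer of 20, reject at 8 or more of 40. At a rate of 10%, P(8 or more of 40) is 4.19%, or 4.12% once the interim stop is included. A limit of 7 would give 9.95%. So 8 is the smallest limit consistent with the stated 0.05. (The stated 80% power at 15% does not reproduce: the exact value is 24.4%. That is a separate matter and plays no part here.)

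**4. What attribution can change.** Let p be the proportion of patients with a related qualifying toxicity and b the proportion with an unrelated one (grade 3 or worse, or persistent grade 2). The documents give no value for b; the values below are assumptions, with independence also assumed.

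- All-cause rate: q = 1 − (1 − p)(1 − b)
- Meeting the interim criterion: (1 − q)^20 + 20q(1 − q)^19
- Rejecting: sum over x = 2 to 20 of P(X1 = x) × P(X2 ≥ 8 − x), with X1 and X2 each Binomial(20, q)

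For p = 0.10 and b = 0.01, q = 1 − 0.90 × 0.99 = 0.109. The chance of meeting the interim criterion is 0.0994 + 0.2433 = 0.343, and the chance of rejecting is 0.063.

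| p | b (assumed) | q | Meets interim criterion | Rejects (8 or more, after passing the interim) |
|---|---|---|---|---|
| 10% | 0 (related only) | 10.0% | 39% | 4.1% |
| 10% | 1% | 10.9% | 34% | 6.3% |
| 10% | 2% | 11.8% | 30% | 9.1% |
| 10% | 3% | 12.7% | 26% | 12.6% |
| 10% | 5% | 14.5% | 19% | 21% |
| 5% | 0 (related only) | 5.0% | 74% | 0.07% |
| 5% | 1% | 5.95% | 66% | 0.2% |
| 5% | 2% | 6.9% | 59% | 0.5% |
| 5% | 3% | 7.85% | 53% | 1.1% |
| 5% | 5% | 9.75% | 41% | 3.6% |

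**The case against.** The removal contradiction has no good defence. The case against the second part is stronger.

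- **The text leans one way.** Section 5.0 takes the endpoint's own two categories and disregards attribution for the grade 3 or worse one. Sections 3 and 11.1 do the same for reporting, and section 11.1 ties this to an FDA request. A reader might infer two rival definitions of the endpoint; the documents do not support that. They show an ambiguity, since no passage states a competing count. Nor does the removal conflict define the count.
- **The test is not wholly silent.** The abstract's gloss on the null links it to the dose, and by usage DLT seems to mean the qualifying toxicity. Both are fair points, but neither selects levels on the section 11 scale.
- **Both counts can be rebuilt.** Attribution is recorded per event and all events reach the FDA. This limits the harm but does not replace naming the primary count in advance.
- **The size is easily overstated.** At a related rate of 10%, the interim stands at exactly one event in 27% of trials, and the final count at exactly seven in 5.5%. A reader might take these as the chance that one unrelated event changes the outcome, with no background rate needed. That is wrong: the unrelated event must also occur in another patient. At an assumed 1%, the figures become 0.270 × (1 − 0.99^19) = 4.7% and 0.055 × (1 − 0.99^33) = about 1.6%.
- **The interim rule is permissive.** The study can stop, and the abstract makes proceeding depend on DSMB review. The interim column shows the chance of meeting a criterion, not of stopping.
- **Rejecting more often need not be an error.** If the 10% null is all-cause, 10% related plus 5% unrelated is a true 14.5%, and rejecting 21% of the time is power. It is inflation only under a drug-related null.

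**Conclusion.** The removal rule is wrong as written. Three statements give two incompatible conditions for grade 3 or worse toxicity and must be reconciled; no view is taken on which is right. This conclusion rests on the text alone.

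The attribution basis of the primary count is unsettled and should be clarified. How much it matters depends on a background rate that the documents do not give and on independence of related and unrelated events. At a related rate of 10% the effect is modest for background rates of 1 to 3% and larger from about 5%. The abstract describes a cohort with moderate to severe COPD. However, section 2 lists three recruitment sources, and eligibility requires ECOG 0-1 and excludes unstable cardiac disease and uncontrolled hypertension or diabetes, so a low rate is possible. The figures do not show that the type I error is inflated, because which null is meant is the open question.

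**What to change.** 1. Reconcile the Removal from Study list, the Toxicity Monitoring paragraph and section 11.2.3 into one statement, used in every place.
2. Before the interim, add to section 12 a definition on these lines: *A qualifying toxicity is one of grade 3-4, or of grade 2 lasting over two weeks, [of any attribution / judged possible, probable or definite on the section 11 scale].* Choose one option, and state that the 10% null, the limit of 1 in 20 and the limit of 8 in 40 all use it.
3. Replace DLT with that term, and align the abstract's Primary Endpoints and Brief Statistical Section and the section 3 objective.
4. Tabulate the count on the other basis beside the primary one at both looks.

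The cost is a few sentences and matching edits. No extra patients or data are needed, because section 11 already has attribution recorded for each event.
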